7.2. Exclusion Criteria

1. Subjects with an active infection
2. Subjects with history of recurrent (> 1) pulmonary embolism or deep vein thrombosis
3. Subjects who, in the Investigator's opinion, are unable to tolerate a right heart catheterization
4. Subjects who have had a major cardiovascular event (e.g., myocardial infarction, open heart surgery, stroke, etc.) within 2 months of Baseline Visit
5. Subjects with Cardiac Resynchronization Device (CRT) implanted < 3 months prior to enrollment
6. Subjects with a Glomerular Filtration Rate (GFR) < 25 ml/min (obtained within 2 weeks of the baseline visit) who are non-responsive to diuretic therapy or who are on chronic renal dialysis
7. Subjects with congenital heart disease or mechanical right heart valve(s)
8. Subjects who have received a Ventricular assist device (VAD) or are likely to undergo heart transplantation or VAD within 6 months of baseline visit.
9. Subjects with known coagulation disorders
10. Subjects with a hypersensitivity or allergy to aspirin, and/or clopidogrel

7.3. Study or Site Termination

This confidential document is the property of Abbott and shall not be reproduced, distributed, disclosed or used without the express written consent of Abbott

Clinical Investigation Plan

The Sponsor or the Investigator has the right to discontinue the study at any time. As much as possible, this should occur after mutual consultation. The Investigator (or sponsor, where appropriate) is responsible for informing the Institutional Review Board (IRB) of trial closure.

Conditions may arise during the study that could prompt termination of the study or the study sites. Conditions that may prompt such considerations include, but are not limited to, the following:

- The discovery of unexpected serious, or unacceptable risk to the subjects enrolled in the study
- A decision on the part of Sponsor to suspend, discontinue, or shorten the study
- Study conduct at the study site may warrant termination under conditions that include the following:
 - Failure of Investigator(s) to enroll eligible subjects into the study
 - Failure of Investigator(s) to comply with the Food and Drug Administration (FDA) regulations
 - Submission of false information from the research facility to Sponsor, the Clinical Monitor, or a regulatory authority
 - Insufficient adherence to protocol requirements
 - A conflict of interest of the Investigator, his/her institution, or site personnel that would negatively impact the integrity of the clinical trial
 - Institution or IRB under investigation for cause by a federal agency

STUDY PROCEDURES

All subjects will be followed for 2 years. A subject is considered to have successfully completed the study upon completion of the 2 year visit (see Appendix B for the Schedule of Events).

8.1. Screening Visit

During the screening visit, the following procedures/assessments will be performed to determine subject eligibility:

- Informed Consent prior to the conduct of any study-related procedures
- Physical examination including vital signs (temperature, heart rate, respiratory rate, blood pressure), weight, height, BMI calculation (refer to Appendix H)
- Medical and surgical history including ejection fraction data must be taken within the last 3 months to enroll in the study.
- Patient history of heart failure hospitalizations in the 12 months previous to the baseline visit as documented in information provided by the patient's cardiologist, internist, or referring physicians and review of all source documents of any heart failure hospitalization(s) reported in the previous year.
- Demographics

This confidential document is the property of Abbott and shall not be reproduced, distributed, disclosed or used without the express written consent of Abbott

Clinical Investigation Plan

- NYHA Functional Classification
- Calculation of GFR (requires creatinine - refer to Appendix I)
- Assessment of medications
- Kansas City Cardiomyopathy Questionnaire-12 (KCCQ-12) (refer to Appendix E)
- Brief Illness Perception Questionnaire (refer to Appendix F)
- Cardiac Health Security Survey (refer to Appendix G)
- Assessment of enrollment eligibility (inclusion/exclusion criteria)

The study coordinator or designee will administer patient-reported outcome questionnaires. It is important that the subject understands the meaning of all words and instructions in each questionnaire and answers all the questions. The subject will be instructed to ask any questions about the questionnaire if further explanation is needed. The research coordinator or designee will review the questionnaires to verify that all questions have been answered. The measures used will be the Kansas City Cardiomyopathy Questionnaire-12 (KCCQ-12), the Brief Illness Perception Questionnaire, and the Cardiac Health Security Survey. The Patient Reported Outcomes will be obtained at screening and each follow up visit post implant (with the exception of the 1 month follow-up visit) for 2 years. Patients who were enrolled in the study prior to addition of patient reported outcome questionnaires, and therefore did not complete baseline questionnaires, are not required to complete questionnaires at the follow-up visits.

Eligible subjects will be scheduled for the Implant procedure. Subjects on anticoagulation therapy (e.g. warfarin) may be instructed by the Investigator to discontinue use 1-2 days prior to pressure sensor placement. The investigator should consider utilizing enoxaparin (Lovenox) per the site's standard of care as bridge therapy to Sensor placement in subjects who were on anticoagulation therapy.

For subjects at risk for gastro-intestinal bleeding during the period in which dual antiplatelet therapy is given, the investigator should consider a proton pump inhibitor such as omeprazole (Prilosec). Subjects at risk include the elderly, those with a history of gastroduodenal ulcers, gastroesophageal reflux disease, esophagitis, intestinal polyps or cancer. Subjects who smoke or who are using steroids or non-steroidal anti-inflammatory drugs may also be at risk.

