7.1. Inclusion Criteria

1. Written informed consent obtained from subject or legal representative
2. ≥ 18 years of age
3. Diagnosis of NYHA Class III Heart Failure *Note: Subjects who are on continuous inotropic therapy should be considered in Stage D refractory heart failure and are not eligible for enrollment in the study.*
4. At least 1 HF hospitalization within 12 months of Baseline visit
5. Subjects with reduced LVEF heart failure should be receiving a beta blocker for 3 months and an ACE-I or ARB for one month unless in the Investigator's opinion, the subject is intolerant to beta blockers, ACE-I or ARB.
6. Subjects with a BMI ≤ 35 . Subjects with BMI >35 will require their chest circumference to be measured at the axillary level, if > 65 inches the patient will not be eligible for the study.
7. Subjects with pulmonary artery branch diameter ≥ 7 mm - (implant target artery - assessed during the RHC)
8. Subjects willing and able to comply with the follow-up requirements of the study

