8.2. Right Heart Catheterization and Implant Procedure (Baseline Visit)

Before the RHC, the following procedures/assessments will be performed:

- Abbreviated physical examination (i.e., vital sign assessments and significant changes since Screening Visit) and weight
- Confirmation of enrollment eligibility (other than angiographic criteria)
- PT/PTT with International Normalized Ratio (INR) of 1.5 or less for subjects previously on warfarin
- Assessment of heart failure medications
- Record any medical history updates since screening visit.

This confidential document is the property of Abbott and shall not be reproduced, distributed, disclosed or used without the express written consent of Abbott

Clinical Investigation Plan

The patient will then undergo a standard RHC. A selective, hand injected pulmonary angiogram will be performed via the pulmonary artery catheter to identify a suitable pulmonary artery branch for sensor implantation. Subjects must have an appropriately sized ($\geq 7\text{mm}$ diameter) pulmonary artery branch. Subjects who do not meet this inclusion criteria will not receive the PA Sensor implant and will be considered ineligible for the study. These subjects will be documented as consented not implanted and will be followed for 30 days for safety. Patients with a suitable target pulmonary artery branch will undergo:

- Wireless implantable hemodynamic sensor implant
- Pulmonary artery catheter measurements (pulmonary systolic, pulmonary diastolic, pulmonary mean, cardiac output) done 3 times consecutively with sensor measurements for setting of sensor baseline.
- Provide post-procedure vascular access site care per standard procedure
- At the Investigator's discretion, subjects should be discharged once stable with respect to the procedure and their heart failure.
- Please see User's Manual for implant details

Subjects who are currently on anticoagulant therapy (warfarin, or any FDA approved anticoagulant) will restart treatment. The subject's INR should be checked periodically to ensure that it is in the therapeutic range. Those subjects not on chronic warfarin will be placed on anticoagulant/antiplatelet therapy as indicated in the device User's Manual. Refer to the User's Manual for further details.

8.3. Study Follow-Up Visits 1, 2, 3, 4, and 5 (Months 1, 6, 12, 18, and 24)

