Implanted subjects will be evaluated at Month 1 (± 7 days) and at Months 6, 12, 18, and 24 (± 30 days) and the following procedures/assessments will be performed:

- Updated medical and surgical history
- Assessment of AEs that occurred since the last visit
- Abbreviated physical examination (significant changes since previous visit) including vital signs (heart rate, respiratory rate, blood pressure), and weight
- Assessment of NYHA functional class
- Kansas City Cardiomyopathy Questionnaire (KCCQ-12)
- Brief Illness Perception Questionnaire
- Cardiac Health Security Survey
- Heart failure medication review
- PA pressure measurements may be obtained at the Investigator's discretion

This confidential document is the property of Abbott and shall not be reproduced, distributed, disclosed or used without the express written consent of Abbott

Clinical Investigation Plan

Subjects will be reminded to obtain pulmonary artery pressure measurements utilizing the CardioMEMS HF System as directed. Subjects will be reminded of the current ACC/AHA guidelines regarding sodium and fluid restrictions.

The study coordinator or designee will administer patient-reported outcome questionnaires. It is important that the subject understands the meaning of all words and instructions in each questionnaire and answers all the questions. The subject will be instructed to ask any questions about the questionnaire if further explanation is needed. The research coordinator or designee will review the questionnaires to verify that all questions have been answered. The Patient Reported Outcomes will be obtained at 6, 12, 18 and 24 months. Patients who were enrolled in the study prior to addition of patient reported outcome questionnaires, and therefore did not complete baseline questionnaires, are not required to complete questionnaires at the follow-up visits.

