Patient improvement in Quality of Life will be reported. The difference between the Quality of Life scores at 6 months, 12 months, 18 months, and 24 months will be compared to the baseline values using general linear mixed models. Quality of Life will be measured using the Kansas City Cardiomyopathy Questionnaire-12 (KCCQ-12), the Brief Illness Perception Questionnaire, and the Cardiac Health Security Survey.

PAS SUB-STUDY

This section describes the design, hypotheses, populations, endpoints and analysis of the PAS sub-study. All other sections of the protocol pertain to the main PAS cohort unless specifically stated otherwise.

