APPENDIX B: Schedule of Events

	Screening	Baseline (Implant)	Month 1	Months 6 and every 6 Months thereafter until Study Termination
Procedures		(within 30 days of Screening)	Visit 1 (30 ± 7 days)	Visits 2-5 or Study Termination (± 30 day window)
Informed Consent	X			
Demographics	X			
Past Medical & Surgical History	X			
Inclusion/Exclusion Criteria Review	X	X		
GFR	X			
Kansas City Cardiomyopathy Questionnaire (KCCQ-12)	X			X
Brief Illness Perception Questionnaire	X			X
Cardiac Health Security Survey	X			X
INR (if indicated)		X		
Pulmonary artery measurement		X		
Physical Examination (including weight)	X ¹	X ²	X ²	X ²
NYHA HF Classification	X		X	X
Pulmonary Artery Angiography		X		
Sensor Implant		X		
Sensor Measurements		X	X (Investigator discretion)	X (Investigator discretion)
Adverse Events Assessment		X	X	X
Medication Assessment (heart failure)	X	X	X	X

¹ Includes weight, height and vital signs (temperature, blood pressure, pulse, respirations).

² Includes weight, vital signs and significant changes from previous physical examination

Clinical Investigation Plan

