APPENDIX E: Kansas City Cardiomyopathy Questionnaire-12

Kansas City Cardiomyopathy Questionnaire (KCCQ-12)

The following questions refer to your heart failure and how it may affect your life. Please read and complete the following questions. There are no right or wrong answers. Please mark the answer that best applies to you.

1. Heart failure affects different people in different ways. Some feel shortness of breath while others feel fatigue. Please indicate how much you are limited by heart failure (shortness of breath or fatigue) in your ability to do the following activities over the past 2 weeks.

Activity	Extremely Limited	Quite a bit Limited	Moderately Limited	Slightly Limited	Not at all Limited	Limited for other reasons or did not do the activity
a. Showering/bathing	0 1	0 2	0 3	0 4	0 5	0 6
b. Walking 1 block on level ground	0	0	0	0	0	0
c. Hurrying or jogging (as if to catch a bus)	0 1	0 2	0 3	0 4	0 5	0 6

2. Over the past 2 weeks, how many times did you have swelling in your feet, ankles or legs when you woke up in the morning?

Every morning	3 or more times per week but not every day	1-2 times per week	Less than once a week	Never over the past 2 weeks
0	0	0	0	0
1	2	3	4	5

3. Over the past 2 weeks, on average, how many times has fatigue limited your ability to do what you wanted?

All of the time	Several times per day	At least once a day	3 or more times per week but not every day	1-2 times per week	Less than once a week	Never over the past 2 weeks
0	0	0	0	0	0	0
1	2	3	4	5	6	7

4. Over the past 2 weeks, on average, how many times has shortness of breath limited your ability to do what you wanted?

All of the time	Several times per day	At least once a day	3 or more times per week but not every day	1-2 times per week	Less than once a week	Never over the past 2 weeks
0	0	0	0	0	0	0
1	2	3	4	5	6	7

5. Over the past 2 weeks, on average, how many times have you been forced to sleep sitting up in a chair or with at least 3 pillows to prop you up because of shortness of breath?

Every night	3 or more times per week but not every day	1-2 times per week	Less than once a week	Never over the past 2 weeks
0	0	0	0	0
1	2	3	4	5

Rev. 2012-04-11

This confidential document is the property of Abbott and shall not be reproduced, distributed, disclosed or used without the express written consent of Abbott

Clinical Investigation Plan

KCCQ-12
Page 2 of 2

6. Over the past 2 weeks, how much has your **heart failure** limited your enjoyment of life?

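### The KCCQ-12 baseline has no minimum time since the last HF admission, so ordinary recovery after that admission cannot be separated from the reported change

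*Combined protocol and SAP*

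**What the plan says.** Inclusion criterion 4 (section 7.1) asks for "At least 1 HF hospitalization within 12 months of Baseline visit". That is an upper limit only. No section sets a minimum interval between HF discharge and screening, or between HF discharge and the questionnaires.

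The quality-of-life baseline is the screening visit (section 8.1): "The Patient Reported Outcomes will be obtained at screening and each follow up visit post implant", with Month 1 left out. Appendix B places the implant "within 30 days of Screening". Section 8.3 gives the later assessments: "The Patient Reported Outcomes will be obtained at 6, 12, 18 and 24 months". In Appendix E, seven of the eight numbered KCCQ-12 questions refer to the past 2 weeks; question 1, for example, asks about limitation "in your ability to do the following activities over the past 2 weeks". Question 7 is the exception.

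Section 12.7.2 announces a report of improvement in quality of life. Scores at 6, 12, 18 and 24 months "will be compared to the baseline values using general linear mixed models". It names no control, no covariate and no sensitivity analysis for this comparison.

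**The concern.** Every subject is selected for an HF admission in the past year, is scored at an unrestricted time after it, and is then compared only with that score. A KCCQ-12 completed within a few weeks of discharge describes, in part, the episode and the convalescence. By Month 6 such a subject would be expected to have recovered to some degree whatever the device does. With no score between screening and Month 6, the trajectory cannot separate early recovery from later change. With no comparison group and no term for time since discharge, the model cannot separate them either.

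At stake is how the KCCQ-12 result is read. It is a supplemental analysis without a hypothesis or success criterion, so the primary safety and effectiveness endpoints do not depend on it.

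**Working it through.** The plan gives no SD, effect size, power or sample size for quality of life, so there is no figure to reproduce. The check has two parts.

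**1. Is there anything in the documents that would keep recovery out of the change score?**

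- Eligibility: the only washouts are 2 months after a major cardiovascular event and 3 months after CRT implant (section 7.2). Criterion 5 of section 7.1 sets drug durations for reduced-LVEF subjects and does not refer to the admission.
- Timing: the questionnaire may precede the implant by up to 30 days (Appendix B), and the next one is at Month 6.
- Control: the historical self-control in the synopsis is for effectiveness. It supplies no earlier quality-of-life score.
- Model: section 12.7.2 names no covariate.

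Nothing found removes or isolates the recovery.

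**2. How large could it be?** All inputs here are assumptions, except the alpha of 0.05 two-sided (section 12) and the 1200 subjects and 49.1% attrition (section 12.2).

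Share of subjects close to the admission, if one admission falls uniformly over 12 months:

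- within 30 days: 30/365 = 8%
- within 60 days: 60/365 = 16%
- within 90 days: 90/365 = 25%

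Mean rise with no device effect = share × recovery, taking recovery of 5 to 15 points:

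- lowest: 0.08 × 5 = 0.4 points
- highest: 0.25 × 15 = 3.75 points
- if half the subjects were recent: 0.50 × 5 = 2.5 to 0.50 × 15 = 7.5 points

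Chance of a significant rise with no device effect, by a one-sample normal approximation: Φ(m√n / S − 1.96), where m = share × recovery, S² = SD² + share × (1 − share) × recovery², and SD of change is 20 or 25. For n, 1200 × (1 − 0.491) = 611.

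Example with share 25%, recovery 10 and SD 20: m = 2.5; S = √(400 + 0.1875 × 100) = 20.46; 2.5 × 24.72 / 20.46 − 1.96 = 1.06; Φ = 86%.

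| Share recent | Recovery (points) | Mean rise | Chance, SD 20 | Chance, SD 25 |
|---|---|---|---|---|
| 8% | 5 | 0.4 | 7% | 6% |
| 16% | 10 | 1.6 | 49% | 35% |
| 25% | 10 | 2.5 | 86% | 68% |
| 50% | 10 | 5.0 | above 99% | above 99% |

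With no recovery at all the chance is 2.5%.

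The n of 611 is only a convenient size. Subjects enrolled before the questionnaires were added contribute no scores (section 8.1) and their number is not given. Section 12.2 also prints 49.1% beside 228/550, which is 41.5%. For SD 20 the four rows give 5%, 28%, 56% and 99% at n = 300, and 10%, 78%, 99% and above 99% at n = 1200.

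**The case against.** The strongest objections are these.

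- **Exclusion 4 may already impose a gap.** It removes "Subjects who have had a major cardiovascular event (e.g., myocardial infarction, open heart surgery, stroke, etc.) within 2 months of Baseline Visit". If the open-ended list took in an HF admission, there would be a 2-month gap. But HF hospitalization is not listed and Appendix J does not define the term. On that reading the gap would run to the implant, so a questionnaire completed up to 30 days earlier could still fall about one month after the event.
- **NYHA Class III narrows the group.** Class is assessed at the same screening visit, and Appendix C puts subjects with symptoms at rest in Class IV. An inpatient still symptomatic at rest would not qualify. This stands, and it makes a large in-hospital share less likely. It does not exclude a recently discharged Class III subject.
- **The argument covers one instrument.** The 2-week recall belongs to the KCCQ-12. The Brief Illness Perception Questionnaire and the Cardiac Health Security Survey print no such recall and largely ask about beliefs, control and information. This stands, and the point is limited to the KCCQ-12.
- **The plan does not attribute the change to the device.** True of section 12.7.2. But a result announced as improvement, with no control, invites that reading.

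A reader might also infer from section 8.2 that subjects are implanted while their HF is unstable, because "subjects should be discharged once stable with respect to the procedure and their heart failure". The documents do not support that. The sentence is a post-implant discharge instruction, left to the investigator's discretion, and says nothing about the subject's state when the questionnaire was completed. It shows only that implant near an HF episode is not ruled out.

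**Conclusion.** The point holds for the KCCQ-12. Recovery in recently discharged subjects is included in the reported change, and the plan has no step that would separate it or show how much of it there is. It is a minor point: a supplemental analysis is affected and no primary endpoint is.

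The size cannot be established from the documents. Under the uniform-admission assumption with 5 to 15 points of recovery, the mean rise is 0.4 to 3.75 points; if half the subjects are recent, it is 2.5 to 7.5 points. That runs from negligible to large, depending on a timing distribution that the documents do not give.

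A reader might go further and conclude that the plan will produce a false-positive quality-of-life result. That does not follow. The share of recent subjects, the recovery, the SD and the number with scores are all assumed; at the low end the chance of a significant rise is only 6 to 7% with n = 611; and section 12.7.2 sets no success criterion that could be falsely met.

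**What to change.** In section 12.7.2, for the KCCQ-12:

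1. Derive the time from last HF discharge to the screening questionnaire, in strata fixed in advance (for example in hospital or 30 days or less, 31 to 90 days, over 90 days), and report its distribution.
2. Add this variable and its interaction with visit to the mixed model, and report change from baseline in each stratum. The interaction is essential: if baseline is one of the modeled visits, a main effect alone shifts the level of the scores and leaves the change untouched.
3. Prespecify a sensitivity analysis that excludes recently discharged subjects. It should not replace the main result. Restricting the headline to the over-90-day stratum would drop subjects who are within the indication (section 4.3) and would still be an uncontrolled before-after comparison.
4. Describe the overall result as change from baseline, without attributing it to the device.

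This changes the analysis only. Appendix A anticipated complete enrollment by December 2017 and version C is dated 19 February 2018, so the analysis is the practical place to act.

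The cost is plan wording and one derived variable. Intervals within strata will be wider, and the headline change may be smaller. Section 8.1 has prior-year HF hospitalizations reviewed from source documents but does not say that discharge dates are entered in the database; the sponsor must confirm that they are.
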